3. STUDY DESIGN

3.1. Study Schema

Description

This is a single-center, phase I/II, randomized, prospective, double-blinded, placebocontrolled study of FMT in the treatment of active pediatric UC. The primary aim is to assess safety and feasibility of a weekly FMT maintenance therapy. A total of 60 patients with active UC (as defined by PUCAI score of > 9) will be enrolled and randomized to first receive FMT or placebo (study treatment).

For therapy/placebo induction, a retention enema will be administered according to the treatment arm to which the patient is assigned. FMT by retention enema will afford us the best delivery method equivalent to that previously described by Moayyeddi and Kunde (see Background) for engraftment of donor stool using FMT materials available to us. Subsequent administrations will occur as oral, frozen encapsulated inocula/placebo for 7 weeks. After the first 8 weeks, subjects will have the option to continue on study treatment or switch to open-label FMT. Subjects will be followed by telephone to assess adverse events for a total of 6 months after their last FMT dose.

Patient metadata and stool samples will be collected at key time points. The patient-reported metadata collection technique will allow for numerous clinical correlations to be parsed out using the random forest machine learning capabilities of synthetic learning in microbial ecology (SLiME) to identify taxonomic features associated with important clinical parameters.(22)

An initial subset of 10 subjects will be enrolled in the study (will be limited to only those patients 12 years of age or older and to those who have mild to moderate ulcerative colitis) and randomized to receive FMT or placebo. We'd expect short term adverse events to occur within 7 days of FMT administration. Individual subject safety data will be reviewed by the PI to assess whether FMT appears to be safe in the subject before continuing the subject towards open-label use of FMT.

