5.2.3. Open-label FMT or Follow-up

After completing 8 weeks of blinded study treatment, study subjects will be given the option to receive open-label maintenance FMT weekly for the remainder of the study if they initially received placebo and did not improve OR if they received FMT, improved, and wish to continue treatment. Subjects will be considered to have improved if their PUCAI score shows improvement of at least 10 points compared to baseline or a score of 10 points or less.

After a subject receives the last dose of blinded study treatment at week 8, the subject's treatment assignment will be unblinded to determine the appropriate course of action. Those subjects, who 1) are found to have improved after receiving 8 weeks of placebo or 2) are found not to have improved after receiving 8 weeks of FMT, will not be eligible to receive open-label FMT. Those subjects will be considered in follow up and will have disease status assessments conducted weekly for the 1st month and then monthly for the following month or 5 months. Subjects will also collect a stool sample and have medical examinations done at 3 and 6 months after their last dose of FMT.

Study subjects who are eligible and interested in continuing on to open-label FMT can be enrolled within 14 days (\pm 7 days) following blinded treatment completion. For the open label phase, subjects who received active treatment (FMT) will proceed directly to open label treatment weekly capsules. However, subjects randomized to placebo (aka no antibiotics, no FMT) will undergo a 7-day antibiotic conditioning and a 2-day rest period prior to commencing open-label FMT treatment that will begin with a retention enema. Thereafter, all subjects will return weekly for observed FMT administration as previously described, AE assessment and survey and stool collection. Routine laboratory assessments and medical exams will be conducted monthly. At all times during this study, standard of care progression of medical/surgical therapy will be offered if clinical course dictates it is necessary for both FMT and placebo arms of the study.

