5.3.3. Clinical Outcomes

Primary Outcome Measures

- 1. Presence of FMT-related adverse events grade 2 or above.
- 2. Proportion of subjects with any FMT-related adverse events of grade 2 or above at 8 weeks post-FMT. Patient related outcomes of rectal bleeding and number of bowel movements. Rectal bleeding will be assessed using common language from PUCAI scoring. (See Figure 1)

Figure 1.

Rectal Bleeding
None
Small amount only, in less than 50% of stools
Small amount with most stools
Large amount (> 50% of stool content)

Secondary Outcome Measures

- 1. Remission as defined by PUCAI of ≤ 9
- 2. Improvement in inflammatory biomarkers (stool calprotectin, serum ESR/CRP, albumin, Hematocrit).
- 3. Changes in gut microbial composition.
- 4. Improvement of PUCAI of \geq 20 points. (30)
- 5. Assessment of engraftment of donor microbes into recipients.

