6. SAFETY ASSESSMENT

6.1. Adverse Event Assessment and Reporting

Comprehensive assessments of any apparent adverse event(s) (AE) experienced by the study subject will be performed throughout the course of the study.

The PI will submit reports of unexpected Serious adverse events (SAEs) and other unanticipated problems to the Institutional Review Board (IRB) at Boston Children's Hospital and to OpenBiome according to their policies.

The PI will report events that are both serious and unexpected and that are associated with FMT/study intervention to the FDA and other applicable health authorities within the required timelines as specified in 21 CFR 312.32 (IND Safety Reports).

The following unexpected AEs will be assessed, recorded and reported to the Data Safety Monitoring Board (DSMB) on an expedited basis: all SAEs, AEs grade 3 (according to CTCAE 5.0 (31) if applicable) or above, and any unexpected AEs grade 2 or above that is possibly or probably related to FMT (as determined by a blinded investigator). Only an AE that meets the above criteria will be recorded and reported. Each reported AE will be described by its duration (i.e., start and end dates), regulatory seriousness criteria if applicable, expectedness, suspected relationship to the study treatment, and actions taken (a blinded investigator will determine expectedness, severity and relationship to study treatment).

Individual subject participation will be temporarily halted until the DSMB determines appropriateness of re-initiation of therapy in any subject experiencing an adverse event resulting in: an Emergency Department visit that is possibly or probably related to FMT, significant worsening of their disease, or experiences 1 SAE Grade \geq 3.

Individual subject participation in the study will be permanently stopped if a SAE Grade ≥ 3 is deemed possibly or probably related to FMT, including any hospital admission.

If 2 or more subjects experience 1 SAE grade \geq 4, all study activities will be halted until the DSMB determines appropriateness of re-initiation of therapy in any subject.

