7. STATISTICAL CONSIDERATIONS

7.1. Power Calculation

The primary aim of this phase I/II study is to establish whether or not FMT is a safe treatment for children and young adults with UC. Based on clinical experience, adverse events (AEs) in IBD patients are common and include abdominal pain, cramping, diarrhea, fever, bloody stool, vomiting, frequent defecation, joint pain, and eye pain. It's estimated that 70% of patients in any given year will experience a flare of their disease and have some or a combination of these symptoms. Safety, therefore, needs to be assessed relative to the high prevalence of AEs in this population. For the primary outcome, we will take any new reported SAEs or worsening of the existing AEs during the study period following enrollment into account.

The study will be powered for equivalence in the proportion of new SAEs or worsening of the existing AEs, assuming null (Ho) and alternative (Ha) hypotheses defined as follows:

$$\begin{split} & \text{Ho: } p1-p2 \leq \text{-}\delta_L \ \text{ or } p1-p2 \geq \delta_U. \\ & \text{Ha: } \delta_L \leq p1-p2 \leq \delta_U \end{split}$$

where p1 is the proportion of new SAEs or worsening of the existing AEs in the placebo group, p2 is the proportion in the FMT group, δ_L is the lower margin and δ_U is the upper margin. We expect to enroll a total of 60 patients into this study for a total of 30 FMT and 30 placebo patients. Assuming the rate of new incident SAEs or worsening of existing AEs in the placebo group is 10%, there will be 82% power to reject Ho that the difference in proportions is 0.20 or greater from zero in the same direction. Similarly, we will have an 85% power to reject a difference of 0.25 or greater if the rate of new incident SAEs or worsening of existing AEs increases to 15%.

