7.3. Data Analysis

All patients who are eligible, randomized, and have received at least one-dose of the study medication including antibiotics/placebo in the first week will be included into the analysis for primary outcomes to assess the safety and tolerability of FMT, as this will be a per protocol (and not intent-to-treat) analysis . Continuous variables will be presented as mean and standard deviation (SD) or median and interquartile range (IQR), depending on the distribution of the data. Categorical variables will be presented as number and percentage. Disease severity (PUCAI) and patient characteristics at baseline will be compared between the treatment groups to determine whether or not randomization resulted in balanced groups. Methods of 2-group comparison will include Student's t-test, the Mann-Whitney test, Pearson chi-square test, and Fisher exact test, depending on the distribution of the variable under consideration. The primary outcome of safety will be assessed via a 2×2 cross-tabulation, where the proportion of patients with new incident SAEs or upgrade of existing AEs in the FMT group will be compared to the proportion in the placebo group. Two one-sided tests for equivalence (32) will be constructed and the overall *P* value taken to be the larger of the lower and upper tests. Statistical significance will be assessed at *P*<0.05.

For the second outcome, we will use longitudinal data analysis methods to investigate changes in inflammatory biomarkers including stool calprotectin, stool lactoferrin, serum ESR/CRP, albumin, and hematocrit over the study period. Generalized Estimating Equations will be performed to examine the association between FMT and changes in these biomarkers.

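### The primary safety 2x2 has no Week 8 cut-off and no rule for switchers, so followed as written it mixes open-label FMT events and unequal follow-up into both arms

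*Combined protocol and SAP*

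**What the plan says.** Section 7.1 defines the primary safety outcome for the power calculation: "we will take any new reported SAEs or worsening of the existing AEs during the study period following enrollment into account". Section 7.3 analyses it in a single 2x2 table, where "the proportion of patients with new incident SAEs or upgrade of existing AEs in the FMT group will be compared" with the placebo proportion by two one-sided tests (TOST). The analysis set is eligible, randomised subjects with at least one dose of study medication, and 7.3 calls this per protocol. Neither section gives a closing date, a censoring rule or a rule for subjects who change treatment.

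Section 5.2.3 describes what follows the blinded phase. Weekly open-label FMT is offered to subjects "if they initially received placebo and did not improve OR if they received FMT, improved, and wish to continue treatment". For those switching from placebo, this is the first active exposure: "subjects randomized to placebo (aka no antibiotics, no FMT) will undergo a 7-day antibiotic conditioning", followed by an FMT enema. FMT continuers go straight to capsules. Unblinding comes "After a subject receives the last dose of blinded study treatment at week 8".

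Adverse events are assessed throughout open-label treatment (5.1, 5.2.3) and for 6 months after the last FMT dose in anyone who received FMT (5.2.4). Subjects not eligible for open-label FMT have weekly contacts for a month and then monthly contacts for either one or five further months (5.2.3).

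**The concern.** The primary aim is the safety of FMT against placebo, and this 2x2 is the only between-group safety analysis planned. Each subject contributes one yes/no outcome to one column. If the window is the whole study and the columns are the randomised arms, a placebo subject whose first event follows open-label FMT counts as a placebo event. An FMT continuer's open-label event counts as an FMT event. Subjects are also observed for different lengths of time, depending on arm and response. The result is a comparison of two treatment pathways, which is not the question posed.

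Two errors are possible. A true excess on FMT could be hidden by events added to the placebo column. Or two arms with equal blinded risk could fail to show equivalence because the columns were pushed apart. An undefined window could also be settled after treatment codes are known.

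**Working it through.** **1. The plan's own figure.** Inputs from 7.1: 30 per arm, 10% placebo rate, margin 0.20. With equal true rates, SE = sqrt(2 x 0.10 x 0.90 / 30) = 0.0775. One one-sided test at 0.05 has power Phi(0.20/0.0775 - 1.645) = Phi(0.937) = 82.6% (stated 82%). For 15% and margin 0.25, SE = 0.0922 and power is 85.7% (stated 85%). Both reproduce as a single one-sided test. The TOST in 7.3 needs both tests to reject. Exact binomial enumeration of the unpooled Wald TOST gives 67.4% at 10% and margin 0.20, which is the baseline for step 4. The gap between 82% and 67% is a separate matter.

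**2. The text side by side.** Section 7.1 runs the window over the study period. The opening of section 5 uses the same term for the whole time on study. Section 5.2.3 puts switching and continuation inside that time. Section 7.3 has one table and no cut-off. Nothing in section 7 separates blinded from open-label events.

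**3. Illustration: true 20-point excess in the blinded phase.** The plan gives none of the following, so they are assumptions:
- FMT risk is 30%, that is, 10% plus the margin.
- A share s = 0.3 to 0.9 of placebo subjects switch.
- A share c of FMT subjects continue.
- Switching and continuing are unrelated to earlier events.
- There are no later background events.

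Added FMT risk q solves 1 - 0.90(1 - q) = 0.30, so q = 0.222.
- Placebo column = 0.10 + 0.90 x s x 0.222 = 0.16 (s = 0.3) to 0.28 (s = 0.9).
- FMT column = 0.30 + 0.70 x c x 0.222 = 0.347 (c = 0.3) or 0.409 (c = 0.7). It stays at 0.30 if continuing adds no risk.

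| Continuers | Apparent excess, s = 0.3 to 0.9 | Chance of declaring equivalence |
|---|---|---|
| Clean window | 20 points | 5.4% |
| Add no risk | 14 to 2 points | 9.3-11.0% |
| c = 0.3, same added risk | 18.7 to 6.7 points | 4.3-6.2% |
| c = 0.7, same added risk | 24.9 to 12.9 points | 1.2-2.4% |

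The last column is the exact TOST enumeration (30 per arm, margin 0.20, one-sided 0.05), taken over s in steps of 0.05. It peaks at 11.0% at s = 0.6 in the no-added-risk row.

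**4. Illustration: equal 10% risk in the blinded phase.** Half of the placebo subjects switch, and each event-free switcher has open-label event probability q. Continuers add nothing.
- q = 0.10: placebo column 0.10 + 0.90 x 0.5 x 0.10 = 0.145, and TOST power falls from 67% to 51%.
- q = 0.30: placebo column 0.10 + 0.90 x 0.5 x 0.30 = 0.235, and power falls to 17%.

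**The case against.** The strongest reply is that an 8-week comparison is plainly meant. Section 3.2.1 has the DSMB judge the first ten subjects after 8 weeks, 4.1.1 speaks of an 8-week randomised part, and 5.3.3 lists "Proportion of subjects with any FMT-related adverse events of grade 2 or above at 8 weeks post-FMT". The term study period is never defined, and assigning switchers to their randomised arm is an inference. This stands as evidence of intent, and on that reading the primary comparison is unbiased. It does not settle the rule. The 5.3.3 item is a different endpoint (FMT-related, grade 2 or above) and is timed from FMT. The per protocol label says who is included. A table with one entry per subject cannot split a switcher's two periods.

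A second reply is that every driver of the illustrations is assumed and the result goes either way. That is correct. The highest figures need continued FMT to add no risk while a first exposure adds 22%. They also ignore background events, although 7.1 expects 70% of patients to flare in a year.

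A reader might also infer that, with a Week 8 cut-off, switchers' first FMT exposures are lost. The documents do not support that. Their events are assessed and go to the DSMB under the criteria in 6.1, and the first outcome in 5.3.3 has no window and could cover them. What is missing is a stated denominator and summary in section 7.

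**Conclusion.** The point holds as a fault in the written rule. Followed literally, with groups as randomised, 7.1 and 7.3 mix open-label FMT events and unequal follow-up into both columns of the primary table. It is tempting to conclude that the trial is biased towards finding FMT safe, or that the sponsor means to count FMT events as placebo events. The documents support neither conclusion. They give no switching or continuation rates, and several sections point to an 8-week comparison.

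The size is therefore illustrative: roughly 1% to 11% for a wrong declaration of equivalence, against 5.4%, and power of 51% or 17%, against 67%, under equal 10% rates with half of the placebo subjects switching. These rest on the assumptions listed with the calculations. The fault is worth correcting because it sits in the primary analysis and the correction is short. If Week 8 was always intended, the change only writes that down.

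**What to change.** In 7.1 and 7.3, state that the primary 2x2 counts events in both arms from the first dose of blinded study medication, conditioning included, through 7 days after the Week 8 dose. It ends earlier only if open-label antibiotics or FMT start. The 7 days are needed because the eighth dose is given at Week 8 and 3.1 says the team would "expect short term adverse events to occur within 7 days of FMT administration". Stopping at the visit would drop one of eight post-dose weeks.

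In 5.2.3, allow no open-label treatment, antibiotics included, before day 7. Enrolment there is already set at 14 ± 7 days, so the earliest is 14 - 7 = day 7. Antibiotics must be named because only switchers take them, starting 8 days before their first FMT (5.1). If first FMT were on day 14, conditioning would start on day 14 - 8 = 6 and shorten the tail in one arm only.

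Have the blinded investigator already named in 6.1 adjudicate those 7 days, kept from the Week 8 unblinding. No new assessor is needed.

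Cost: a window sentence in each section, no new visits, and unchanged inputs to the power calculation. The downside is that later events leave the primary comparison.

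Optionally, add a descriptive table of all FMT-exposed subjects, timed from first FMT, split by blinded and open-label first exposure and not compared with placebo. With 30-90% switching (assumed), the exposed number rises from 30 to 39-57. The zero-event one-sided 95% upper limit, 1 - 0.05^(1/n), falls from 9.5% to 7.4-5.1%. Its limits should be stated: the added subjects are placebo non-improvers on open treatment, and 6.1 restricts what is captured ("Only an AE that meets the above criteria will be recorded and reported").

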⁷ IBD Biomarkers (quantitative fecal calprotectin) will be done after study completion from frozen samples taken from every study stool sample.

⁸ A urine pregnancy test should only be obtained on day -8 if one has not been done in the past 30 days.

⁹ The "X" location of stool samples indicates when the stool will be collected from the participant. I.e. stool will be collected from the subject on day -8 and Week 1, Day1 however collection kits will

have been provided to the subject beforehand. Lack of stool sample collection will not constitute a protocol deviation.

¹⁰Subjects in the OL treatment will receive FMT (not placebo)

¹¹ If eligible, subjects in OL treatment will receive selective Antibiotics (no placebo).

¹² If a subject received at least 1 dose of FMP IP.

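### The biomarker GEE has no Week 8 cut-off, so a whole-study fit with one arm effect would not be a valid FMT-versus-placebo comparison

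*Combined protocol and SAP*

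**What the plan says.** **The model.** Section 7.3 investigates "changes in inflammatory biomarkers including stool calprotectin, stool lactoferrin, serum ESR/CRP, albumin, and hematocrit over the study period" and adds that "Generalized Estimating Equations will be performed to examine the association between FMT and changes in these biomarkers". It does not give an end date, say whether FMT means randomised arm or current exposure, name a working correlation, or say how unequal follow-up is handled. This is the only analysis given for secondary outcome 2 in section 5.3.3.

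**Who is sampled after Week 8.** Section 5.2.3 states that after the last blinded dose "the subject's treatment assignment will be unblinded to determine the appropriate course of action". Open-label FMT is offered to subjects "if they initially received placebo and did not improve OR if they received FMT, improved, and wish to continue treatment". Those who "are found not to have improved after receiving 8 weeks of FMT, will not be eligible to receive open-label FMT", and likewise placebo improvers, go to follow-up. Improvement means "improvement of at least 10 points compared to baseline or a score of 10 points or less" on the PUCAI.

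**What is collected.** In the open-label phase "all subjects will return weekly for observed FMT administration as previously described, AE assessment and survey and stool collection". Serum labs are monthly in section 5.2.3 and every 4 weeks in the section 5.1 schedule. Subjects in follow-up give stool at 3 and 6 months after their last FMT dose. Section 5.2.4 and footnote 12 of section 5.1 tie the full follow-up to having received at least one active dose. Footnote 7 of section 5.1 says calprotectin is assayed on "frozen samples taken from every study stool sample", so open-label and follow-up stools are included.

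**The concern.** Through Week 8 the two arms follow the same sampling schedule, and a difference between them can be attributed to assignment. After Week 8 neither condition holds. Whether a subject keeps supplying data depends on arm and PUCAI response together: responders are kept in the FMT arm, non-responders in the placebo arm. The placebo subjects who continue are by then receiving FMT.

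An unweighted GEE needs the availability of records to be unrelated to the outcome, given the covariates in the model. Here availability depends on PUCAI change at Week 8, which the stated model does not contain. If the biomarkers move with PUCAI at all, that condition fails. What is at stake is the one planned answer to whether FMT changes inflammation.

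**Working it through.** The plan gives no figure for this model, so there is none to reproduce.

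**1. Stools per subject.** From the section 5.1 schedule and the 29-stool maximum in section 5.3.1:
- Blinded phase: Day -8, Week 1 Day 1 and Weeks 2 to 8, which is 9.
- Open-label: 29 − 9 blinded − 2 (open-label Day -8 and Day 0) − 2 (months 3 and 6) = 16 weekly visits. The 36-survey maximum implies the same 16.

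| Group | After Week 8 | Total |
|---|---|---|
| FMT improver, continues | 1 + 16 + 2 = 19 | 28 |
| FMT non-improver | 2 | 11 |
| Placebo non-improver, switches | 2 + 16 + 2 = 20 | 29 |
| Placebo improver (appears to have no later stool) | 0 | 9 |

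**2. Whose records they are.** Take 30 per arm (section 7.1). Assume 40% improve in both arms, every eligible subject continues and every sample is given.
- FMT arm: improvers 12 × 28 = 336, non-improvers 18 × 11 = 198. Improvers supply 336/534 = 63%.
- Placebo arm: non-improvers 18 × 29 = 522, improvers 12 × 9 = 108. Non-improvers supply 522/630 = 83%.
- After Week 8 only: FMT improvers supply 12 × 19 = 228 of 228 + 36 = 264 (86%). Placebo non-improvers supply all 18 × 20 = 360, in the open-label phase or after it.

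**3. Bias under independence, no FMT effect.** Let a subject's log biomarker change have SD σ and correlation ρ with PUCAI improvement, and let a share p improve. Under bivariate normality the mean change is −ρσφ/p in improvers and +ρσφ/(1−p) in non-improvers, where φ is the normal density at the p-quantile. Assume σ = 0.8, ρ = 0.5 and p = 0.4, so φ = 0.386.
- Improvers: −0.5 × 0.8 × 0.386/0.4 = −0.386. Non-improvers: 0.5 × 0.8 × 0.386/0.6 = +0.258.
- FMT arm, weighted by records: (336 × −0.386 + 198 × 0.258)/534 = −0.147.
- Placebo arm: (522 × 0.258 + 108 × −0.386)/630 = +0.148.
- Difference: −0.295 log units. Since exp(−0.295) = 0.745, the biomarker looks about 26% lower on FMT.
- The bias scales with ρ: about −0.24 at 0.4 and −0.35 at 0.6.
- With 9 blinded records for everyone the weights are equal in both arms and the difference is 0.

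This sketch lets every record carry the full change and omits time terms. It is the full-uptake case.

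**4. False-positive rates by simulation.** No FMT effect, 30 per arm, one pooled arm term, robust standard errors, two-sided 5%. Assumed: correlation 0.4 to 0.6, 40% improving, 60% to 100% uptake.

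| Data and working correlation | Change persists | Change reverts after Week 8 |
|---|---|---|
| Whole study, independence | roughly 19% to 53%, favouring FMT | bias near zero |
| Whole study, exchangeable | 6% to 17% | bias against FMT |
| Blinded samples only | about 4% to 8% | same data |

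The small excess over 5% on blinded samples reflects the robust standard error in a small trial and simulation error.

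**5. Serum markers.** On the sparser serum schedule, with correlation 0.5, persisting change and 31% or 50% improving, a false FMT benefit appears in 17% to 33% of trials under independence and 7% to 19% under exchangeable, against a nominal 2.5%.

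**6. Coding FMT as current exposure.** With exchangeable correlation and persisting change the bias turns against FMT: +0.04 to +0.21 log units, with 9% to 41% rejections, at most 2% in FMT's favour.

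**The case against.** **The harm depends on a model the plan does not specify.** This is fair. Section 7.3 does not say that one pooled arm coefficient will be fitted. In a whole-study GEE with arm-by-visit terms (no effect, correlation 0.5, 40% improving, persisting change), the Week 8 contrast had bias of only −0.02 and 6.2% rejections, against 4.8% on blinded data. A reader might infer that no whole-study model can answer the question. That goes too far: such a model keeps the Week 8 contrast. The plan does not commit to it, and its later contrasts would still be selected and no longer placebo-controlled.

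**A reader might infer that the GEE will show a benefit when FMT does nothing.** The documents do not support that. They give no correlation between the biomarkers and PUCAI, no persistence of change, no coding and no working correlation. Under some of these choices the bias is negligible or runs against FMT.

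**The inputs are near the upper end.** Open-label treatment is optional, and 29 stools is a maximum. In one set of runs under independence, lowering uptake to 60% cut the false-positive rate from 31% to 22%. That is smaller, but still well above 5%.

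**The sampling can be overstated.** Weekly collection applies to stool only. FMT non-improvers are still seen at months 3 and 6. Section 5.2.3 read alone might suggest two later stools from placebo improvers, but they have no FMT dose to count from, and section 5.2.4 and footnote 12 suggest none.

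**The intended window may be 8 weeks.** Possible, but not written. Section 5 uses the same phrase for the whole of participation, and section 4.1.1 has separate wording for the randomised 8 weeks. If the term were defined once, for sections 7.1 and 7.3 together, as the blinded phase, the window would be settled here too. The coding of FMT and the working correlation would remain open.

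**Conclusion.** The point holds as a defect in the specification of a secondary analysis. As written, section 7.3 admits data that are selected on PUCAI response in opposite directions by arm, and that are no longer FMT versus placebo. A whole-study GEE with a single arm effect is therefore not a valid comparison of the randomised groups.

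The structure of the problem follows from the documents alone. Its size does not. The 19% to 53% and 6% to 17% rates require biomarkers correlated 0.4 to 0.6 with PUCAI improvement, 40% improving equally in both arms, 60% to 100% open-label uptake and change that persists. The biomarker variances are also assumed. Direction in favour of FMT is established only for randomised-arm coding with persisting change, and most clearly under independence. The primary safety comparison is a separate analysis and is not affected by this point. The issue should be corrected before analysis.

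**What to change.** In section 7.3, state that the between-arm GEE:
- codes FMT as randomised arm, with arm-by-time terms;
- uses only samples up to and including the Week 8 visit and before any open-label treatment;
- uses a named working correlation.

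State also that later samples are described separately by actual path (FMT continued, placebo switched to FMT, follow-up only), with no comparison of randomised arms.

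The cost is a few sentences. Fewer records enter the model, but no randomised FMT-versus-placebo information is lost, because that comparison ends at Week 8. Sample collection, assays and the open-label rules stay as they are.
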